1. Determine the feasibility, acceptability and initial efficacy of IMPACT with 60 parent-child dyads in an eight-week pilot randomized controlled trial (RCT).

- a. We will use a priori benchmarks to determine the feasibility of IMPACT based on study eligibility, enrollment, and retention.
- b. Acceptability of IMPACT features and engagement will be determined via exit surveys and semi-structured interviews.
- c. Preliminary effect sizes compared to control will be reported on primary outcomes (asthma responsibility, self-efficacy) and secondary outcomes (medication adherence, asthma control and quality of life).
- d. We will also conduct preliminary testing of dyadic interdependence of asthma responsibility over time.

1.6 Study design. Provide a one-sentence description of the general study design and/or type of methodology.

Your answer will help HSD in assigning applications to reviewers and in managing workload. Examples: a longitudinal observational study; a double-blind, placebo-controlled randomized study; ethnographic interviews; web scraping from a convenience sample of blogs; medical record review; coordinating center for a multi-site study.

This study will use a randomized controlled trial design with two parallel study arms, intervention and control (usual care)

1.7 Intent. Check all the descriptors that apply to your activity. You must place an "X" in at least one box.

This question is essential for ensuring that your application is correctly reviewed. Please read each option carefully.

Descriptor
 1. Class project or other activity whose purpose is to provide an educational experience for the researcher (for example, to learn about the process or methods of doing research).
 2. Part of an institution, organization, or program's own internal operational monitoring.
 3. Improve the quality of service provided by a specific institution, organization, or program.
 4. Designed to expand the knowledge base of a scientific discipline or other scholarly field of study, and produce results that: 
• Are expected to be applicable to a larger population beyond the site of data collection or the specific subjects studied, or• Are intended to be used to develop, test, or support theories, principles, and statements of relationships, or to inform policy beyond the study.

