expected lung functioning, spirometers use a reference database that requires patient details including age, gender, height, weight. The parent will be instructed to input the study # (instead of name), year of birth (not date) to avoid unnecessary PHI disclosure. The study team will coach the child through spirometry and request that the results be sent to the study team (via email or text). Note, study team will make every effort to perform spirometry outside (weather permitting) and remain socially distanced and advised to wear masks for spirometry, since it is considered an aerosolizing procedure.

Next, individual data collection will commence. Parent participants will be provided an iPad with the electronic instruments preloaded and instructed to complete the instruments to the best of their ability. If questions arise, the study team will answer as needed. The study team will then work 1:1 with the child and assist with instrument completion (reading items, if requested). This technique has been used successfully in [name] other prior dyadic study designs to preclude parental interference in child items. Full instrument descriptions and timepoints are outlined in table below. Estimated time burden: Parent: 50-55 minutes; Child: 40-50 (plus 30-40 if cognitives added).

Assignment

REDCap randomization module will be used to assign dyads to groups using an externally generated block randomization scheme (stratified by sex). After surveys are complete, the study team will assign dyads to intervention or control by selecting “randomize” within REDCap and proceeding with the following, depending on assignment:

Control

Dyads assigned to the usual care control group will be advised of their assignment. An information sheet will be provided that outlines the upcoming data collection sessions (T1 at 8 weeks and T2 and 16 weeks) with compensation amounts. They will be advised to keep the spirometer to use in future visits, and more frequently if they choose. The PI will send the parent an asthma control assessment, based upon spirometry and asthma status questions (C-ACT), with interpretation using the national asthma guideline standards. This report may be shared with the child's health care provider, if desired. Finally, the family will be advised that at the end of the 16 week study period, they will be offered access to the IMPACT system, including the app and wearable device, should they wish to use it.

Intervention

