5.4 Data variables. Describe the specific data that will be obtained (including a description of the most sensitive items). Alternatively, a list of the data variables may be uploaded to **Zipline**.

App usage – login date and duration, management goals selected, anticipated barriers, progress reports, asthma check ins, C-ACT scores, spirometer results, reported medication use.

Document Date & Version

04/29/2021

Version 3.3

Researcher Date & Version

08/16/2021

Version 1.2

APPLICATION IRB Protocol

Page 20 of 56

Instrument details

Construct	Instrument	Time	T0	T1	T2
Demographics					
NINR Demographics	Parent (race, ethnicity, marital status, employment); Child (birthdate, education, race, ethnicity, asthma history) (P)	5	X		
Child Weight, Height	Stadiometer (D) to measure child height (for spirometry), Scale (D) to measure child weight	5	X X	X X	X X
Shared Management					
Asthma Responsibility	Asthma Responsibility Questionnaire (ARQ) (P, C): 10-items, 5-point scale to report asthma management task responsibility, higher scores indicate higher asthma management responsibility for child. Established construct validity; IC reliability $\alpha=.78$ (child), $.84$ (parent).	<5	X	X	X
Asthma Management	Brief Illness Perception Questionnaire (BIPQ) (P,C): 8-item scale to assess beliefs about asthma, with higher scores indicating more burdensome perception.	<5	X	X	X
	Beliefs about Medicines Questionnaire (BMQ) (P,C): 10-item, 5-point scale to assess medication beliefs and concerns, with higher scores indicating higher perceived necessity or concerns.	<5	X	X	X
Self-Efficacy	Asthma Management Self-Efficacy (P, C): 13-items (parent) and 12-items (child), 5-point scale assesses asthma self-efficacy, higher scores indicate higher self-efficacy. Construct validity; IC reliability $\alpha=.87$ (child), $.87$ (parent).	<5	X	X	X
Medication Adherence	Medication Adherence Report Scale for Asthma (MARS-A) (P, C): 10-items, 5-point scale assessing reported asthma controller medication adherence. $M \geq 4.5$ indicates adherence; IC reliability $\alpha=.68$ (child); $.74$ (parent).	<5	X	X	X
Family Functioning	Family Assessment Device (P): 60-item validated instrument using 4-point Likert scale, with higher scores indicating worse levels of family functioning.	10-15	X	X	X
Daytime Function & Health Outcomes					

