Secondary outcome analyses will use mixed model ANCOVAs to assess whether the primary outcome variable means, adjusted for baseline scores, differ between intervention and control groups. We predict a group x time interaction such that shared management and health outcome variables (asthma responsibility score, self-efficacy, medication adherence, control, QOL) will increase to a greater extent in the intervention group. Also pursuant to Aim 2, the dyadic effect of the intervention will be tested with the Actor-Partner Interdependence Model^{103,112} using structural equation modeling with full information maximum likelihood estimation (FIML). First, the pattern of missing data will be tested to determine if it is missing at random. The FIML method is superior to listwise deletion of missing data points in terms of producing less biased estimates. Next, intraclass correlations (ICC) will be examined for parent and child asthma responsibility, self-efficacy, and general health scores. The APIM produces estimates of actor effects (Person A's pretest \rightarrow Person A's posttest) and partner effects (Person A's pretest \rightarrow Person B's posttest). Actor effects are estimated while controlling for partner effects, and vice versa. In these analyses, dyadic interdependence is indicated by statistically significant **partner effects** (e.g., parent pretest \rightarrow child posttest, controlling for child pretest). Intervention condition will be entered into the model as a dummy coded variable. For each measure taken from both parent and child (i.e., self-efficacy, asthma responsibility) two APIMs will be compared; one in which all of the paths from child variables are constrained equal to their respective paths from the parent variables, and one in which all paths are unconstrained and thus free to vary. Comparison of the fit of these two models indicates whether the effects emanating from the parent are significantly different from those emanating from the child. Parent-child dyads in IMPACT are expected to show stronger **partner effects** than those in the comparison group.

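### Randomisation is stratified by sex, but neither the ANCOVA nor the APIM includes the stratum, so between-arm standard errors are slightly too wide if sex is prognostic

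*Protocol*

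**What the plan says.** **Design.** Protocol section 5.1, under Assignment: "REDCap randomization module will be used to assign dyads to groups using an externally generated block randomization scheme (stratified by sex". The randomised unit is a parent-child dyad, so two people could supply the stratifying sex, and the sentence does not say which. Block size and allocation ratio are not given.

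**Between-arm analysis.** The SAP plans "mixed model ANCOVAs to assess whether the primary outcome variable means, adjusted for baseline scores, differ between intervention and control groups". Baseline score is the only covariate named.

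**Dyadic analysis.** The APIM has actor and partner pretest paths, and "Intervention condition will be entered into the model as a dummy coded variable". The SAP then compares two versions of the model, "one in which all of the paths from child variables are constrained equal to their respective paths from the parent variables", and one with all paths free. No sex or stratum term appears, and the SAP does not mention stratification at all.

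**Purpose.** Aim 1c (Protocol section 1.5) says: "Preliminary effect sizes compared to control will be reported on primary outcomes". The comparison between arms is therefore the efficacy readout.

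**Where sex is recorded.** The demographics row in Protocol section 5.4 reads "Parent (race, ethnicity, marital status, employment); Child (birthdate, education, race, ethnicity, asthma history" and names sex for neither person. Section 5.1 does have the child's gender or sex at birth entered for spirometry.

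**The concern.** Blocking within sex largely removes chance imbalance in sex between the arms, so the true sampling variance of the arm contrast is lower than under simple randomisation. A model without sex cannot see this. It leaves the variance due to sex in the residual and computes its standard error as if that variance still added noise to the contrast. Confidence intervals are then too wide and p-values too large.

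The scope is limited. The arm estimate is not biased and the false-positive rate is not inflated. A sex effect that is constant over time cancels from the predicted interaction ("We predict a group x time interaction such that shared management and health outcome variables"). The APIM partner paths are not randomised contrasts, so this mechanism does not reach them. What is touched is the adjusted between-arm mean difference and the APIM condition coefficient.

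The undefined stratifier is a separate, practical gap: an analyst who wants to reproduce the stratum cannot tell from the documents which variable to use.

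**Working it through.** The plan states no alpha, power, effect size or variance, so there is no figure of its own to reproduce.

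**Inputs**
- 60 dyads: Protocol section 1.5. At the SAP's 80% retention benchmark, 0.80 × 60 = 48.
- Assumed: two-sided 5% test, 1:1 allocation, blocks of 4 within sex, equal numbers of each sex.
- R² = share of baseline-adjusted outcome variance explained by sex. Not in the documents, so a range is shown.

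**1. Size as a function of R².** With arms balanced on sex:

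SE ratio (model / true) = 1/√(1 − R²)

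Actual alpha = 2 × [1 − Φ(1.96/√(1 − R²))]

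| R² | SE ratio | Actual alpha |
|---|---|---|
| 0 | 1.000 | 0.050 |
| 0.02 | 1.010 | 0.048 |
| 0.05 | 1.026 | 0.044 |
| 0.10 | 1.054 | 0.039 |

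**2. Where in that range.** Suppose sex explains 5% of raw variance equally at baseline and follow-up. Set the within-sex variance to 1, so the sex variance is v = 0.05/0.95 = 0.0526. For within-sex pre-post correlation r, the slope without sex is b = (v + r)/(1 + v). Residual variance is (1 + v) − b(v + r) without sex and 1 − r² with sex.

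For r = 0.5: b = 0.5526/1.0526 = 0.525; without sex 1.0526 − 0.525 × 0.5526 = 0.7625; with sex 0.75; R² = 1 − 0.75/0.7625 = 0.016.

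| r (assumed) | Residual R² | SE ratio | Actual alpha |
|---|---|---|---|
| 0.7 | 0.009 | 1.004 | 0.049 |
| 0.5 | 0.016 | 1.008 | 0.048 |
| 0.3 | 0.026 | 1.013 | 0.047 |

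If sex affects level more than change, the lower half of the first table applies.

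**3. Simulation.** ANCOVA at one follow-up time, 60 dyads, 20,000 runs per setting, no dropout. Power is at an assumed effect of 0.74 residual SD.

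| R² | Type I error without / with sex | Power without / with sex |
|---|---|---|
| 0 | 0.051 / 0.051 | 80.1% / 80.1% |
| 0.02 | 0.047 / 0.050 | 79.0% / 79.5% |
| 0.06 | 0.043 / 0.049 | 77.6% / 79.5% |
| 0.13 | 0.032 / 0.045 | 75.6% / 79.8% |

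The formula in step 1 gives 0.048, 0.043 and 0.036 for the last three rows. Both type I figures in the R² = 0.13 row look low by chance; the 48-dyad run at that R² gave 0.037 without sex and 0.050 with it. In a separate set of 8,000 runs per setting at R² of 0, 0.02, 0.05 and 0.10, the mean arm estimate under no effect was within 0.004 of zero throughout.

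**4. Is stratification the cause?** With unstratified allocation, leaving sex out gave 0.052 at R² = 0.06 and 0.053 at R² = 0.13. The conservatism comes from the mismatch between a stratified design and an unstratified analysis.

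**5. APIM condition term.** An outcome equation with own pretest, partner pretest and condition behaved the same way: 0.039 without sex and 0.051 with it at R² = 0.10. The full structural equation model and the mixed model over both follow-up visits were not fitted.

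**The case against.** The case against is about importance, and much of it stands.

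- **The effect is small.** In the more plausible setting (step 2) standard errors are 0.4% to 1.3% too wide and the test runs at 4.7% to 4.9%. Nothing in the documents supports an R² as high as 0.10, and at R² = 0 there is no effect. This stands and sets the priority.
- **The main deliverables are untouched.** The effect sizes are unbiased, the benchmarks concern recruitment, retention and acceptability, and the SAP ties statistical significance to partner effects only. This also stands. The SAP does still plan a between-arm comparison, and the precision reported with a preliminary effect size depends on its standard error.
- **Dropout weakens within-stratum balance.** It does, slightly. With 20% random dropout at R² = 0.10, actual alpha moved from 0.038 to 0.043 in one simulation and from 0.039 to 0.041 in another.
- **The child's sex is the natural reading.** Spirometry uses it, and Protocol section 2.1 mentions the higher prevalence in boys. The demographics row is only a summary, and the full surveys were uploaded separately, so its silence does not show that sex goes uncollected. That is fair, but no text says that the child's sex is the stratifier.
- **The SAP is brief and older.** It is dated 03/19/2020 and the protocol version 08/16/2021, so the omission may not be deliberate. That explains the mismatch but does not remove it: the SAP names its adjustment, and the stratum is not in it.

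**Conclusion.** The concern holds, as a minor one. The design stratifies on sex and the analysis ignores it, so the between-arm ANCOVA contrast and the APIM condition coefficient carry standard errors that are too wide if sex predicts outcome beyond baseline. The overstatement is 1.0% to 5.4% for assumed R² of 2% to 10%, with actual alpha of about 4.8% to 3.9%. It is more likely near 1% or below if sex mainly shifts level. At the assumed effect, the power lost is about half a point at R² = 0.02 and about two points at R² = 0.06. There is no bias and no inflation of the false-positive rate. The group-by-time interaction is unaffected if the sex effect is constant over time, and the partner paths are unaffected by this mechanism.

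These sizes rest on assumed values for R², block size, allocation ratio and alpha, and on single-time-point models.

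**What to change.** 1. In Protocol section 5.1, state whether the child's or the parent's sex is the stratifier.
2. Add to the SAP: *Each between-arm mixed-model ANCOVA will include the baseline score and the randomisation stratum (sex, as defined in Protocol section 5.1) as fixed effects.*
3. For the APIM, add: *The randomisation stratum will be an exogenous covariate on both the parent and the child posttest; its two paths are left free in both the constrained and the unconstrained model.* This keeps the stratum out of the comparison of parent and child paths, where a child's-sex stratum could otherwise be taken for one of the child variables to be constrained.

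**Cost.** SAP wording and one protocol clarification. The randomisation module must already hold the stratum value, so no new data are needed. Each single-time-point ANCOVA loses one degree of freedom: 60 − 3 = 57 becomes 56 (critical t 2.0025 to 2.0032), or at 48 dyads 45 becomes 44 (2.0141 to 2.0154). Each APIM gains two paths; the stability of the full model at 48 to 60 dyads was not tested.

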Dyads assigned to the intervention group will be advised of their assignment. An information sheet will be provided that outlines the intervention tasks (weekly activities) as well as upcoming data collection sessions and compensation amounts. Next, the study team will assist the parent with accessing/downloading the IMPACT app. The family will be encouraged to follow the onboarding screens once downloaded, including pairing the app with the event marker watch (symptom watch) and spirometer device. The symptom watch is a commercially available event marker button that resembles a wristwatch. Children will be taught to press the button when asthma symptoms occur. These events are stored by the watch and synced with the app when connected to the parent phone's Bluetooth.

IMPACT intervention overview:

- Families will be asked to check in on the child's asthma daily (they may use the app to set SMS notifications, if desired) to review symptoms reported by the watch (tracked in the app dashboard).
- They will also be asked to log in weekly to select asthma shared management goals (provided), anticipated barriers, and problem solving. Each subsequent week, dyads will report on their goal progress and select new goals or retain the previous ones.
- To monitor asthma control, families will be prompted to complete the C-ACT (7 item questionnaire) and for the child to complete spirometry. C-ACT and spirometry scores are tracked in the app dashboard (see image)

- The intervention concludes after 8 weeks. The app is configured such that after the 8-week intervention, the goal-setting/monitoring feature is “muted”, but dyads may continue to use the monitoring features (medication use, symptoms, asthma control).

T1 POST-INTERVENTION ASSESSMENT (8 WEEK)

The study team will schedule the T1 data collection session at week 8. The child will be asked to complete spirometry and export results to the study team, as in T0. Dyads will be asked to complete parent and child instruments outlined in the table below, again using the iPads as described above. Families assigned to the intervention will complete short intervention questionnaires and a brief semi-structured interview. Parent: 65-75 minutes; Child: 60-75 (plus 30-40 if cognitives added).

T2 FOLLOW-UP ASSESSMENT (16 WEEKS)

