Remote protocol (if needed): Should remote study visits be required or preferred by participants, the study team will mail study materials (spirometer, paper tape measure) and arrange for web conferencing sessions via Zoom. A link to the study e-Consent and assent form (with video of the PI reading the assent script) will be sent at that time. Families may complete consent and assent asynchronously. If not completed prior to the web conference, the study team will display the REDCap e-Consent module using screen share and allow the parent time to review and complete. Once completed, the study team will read the study assent to the child. After consent and assent, the parent will be sent a personalized weblink to their visit surveys via REDCap. For child survey data – the study personnel will display the surveys using screen share during the web conference. The child may either use “mouse control” to self-select their responses or verbally indicate their responses and study personnel will enter them. Next, the study team member will assist dyads with connecting the previously mailed spirometer to the parent’s smart phone via Bluetooth and mobile app. The app automatically prompts the user to enter sex at birth, age, height (paper tape measure provided) and weight (based upon recall). The family will be instructed to enter the child’s participant ID in the “name” field. The dyad will follow the app instructions for performing spirometry. The final spirometry report will be emailed to the study email. After baseline measures, dyads will be assigned either to the intervention or control group. For those assigned to the intervention group, the study personnel will remotely assist intervention dyads with downloading IMPACT, pairing the symptom watch and reader with app, and reviewing written instructions for use. For dyads assigned to the control arm, they will keep the spirometer for future study sessions.

Future data collection sessions will use a similar Zoom protocol. Note, optional cognitive evaluations are only available in person.

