Title: Improving Asthma Care Together (IMPACT): A Shared Management Pilot Study

NCT #: NCT04908384

Document Date: 03/19/2020

Statistical Analysis Plan

Data Analysis.

Feasibility. Eligibility, enrollment, and retention (number who complete study) data will be summarized in a study flowchart. A priori feasibility benchmarks include $\geq 60\%$ recruitment (eligible dyads who enroll) and $\geq 80\%$ retention; these benchmarks are based on our previous research (80% recruitment, 86% retention) and similar studies.¹⁰⁶⁻¹¹¹ Study withdrawal reasons and timing will also be reported.

Acceptability. Participants will rate IMPACT acceptability via Acceptability of Intervention (AIM) survey and semi-structured interview. The a priori acceptability benchmark will be $\geq 60\%$ of participants rating IMPACT as acceptable (4 or 5 on AIM, table 3).^{106-108,111} Additional participant acceptability feedback will be documented via an exit interview. Quantitative data will be summarized using descriptive statistics whereas qualitative data will undergo thematic analysis, described above.

Analysis of the primary outcomes (asthma responsibility score, self-efficacy). Descriptive summaries of de-identified data will be transferred into SPSS 24 (IBM Corp, Armonk, NY) for analyses. Distributions of interval and ratio level variables will be checked for normality and transformed as necessary. We will compare characteristics of those who completed the study to those who did not to inform the generalizability of findings. We expect an increase in asthma management responsibility scores and increased dyadic interdependence (i.e. nonindependence of scores between dyads)¹⁰³ between parent and child-reported outcomes over time in the intervention group, suggesting true shared management.

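### Spirometry is coached by staff in person but follows app instructions at remote visits, and only the IMPACT arm is prompted to test at home, so the FEV1:FVC comparison carries avoidable noise and a possible test-familiarity difference

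*Protocol*

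**What the plan says.** **In person.** Protocol section 5.1 (T0, Data collection) states: "The study team will coach the child through spirometry". The T1 paragraph carries this forward: "The child will be asked to complete spirometry and export results to the study team, as in T0". T2 is described as nearly identical to T1.

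**Remote.** In the remote protocol of section 5.1, "the study team member will assist dyads with connecting the previously mailed spirometer to the parent’s smart phone via Bluetooth and mobile app". The next step for the blows themselves is "The dyad will follow the app instructions for performing spirometry". Later remote sessions follow a similar Zoom procedure. Remote visits may be used because of COVID-19 restrictions or because the family prefers them, and sections 2.2 and 4.6 offer them to families outside the three counties.

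**Between visits.** In the IMPACT arm, "families will be prompted to complete the C-ACT (7 item questionnaire) and for the child to complete spirometry"; no frequency is given. For controls, "They will be advised to keep the spirometer to use in future visits, and more frequently if they choose". Section 4.5, on the other hand, says of all families that they will use the device from time to time during the study.

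**Role and analysis.** Spirometry (FEV1:FVC, read against guideline cutpoints) and the C-ACT are the two measures of asthma control (section 5.4). Asthma control is a secondary outcome for which a preliminary effect size against control will be reported (section 1.5, aim 1c). Randomisation is stratified by sex only. The SAP compares arms with mixed-model ANCOVAs adjusted for baseline score. It has no term, sensitivity analysis or quality rule for visit mode, coaching or home testing.

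**The concern.** Spirometry depends on effort. Protocol section 10.1 describes maximal exhalations that may tire or stress a child. Section 5.1 also gives data integrity, and help with new devices including the spirometer, as the reasons for requiring in-person sessions. The remote text nevertheless spells out a live staff role for the child surveys and for pairing the device, but none for the blows.

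Two separate consequences follow.

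1. **Visit mode.** The same measure is obtained under two procedures, and a child may change mode between T0 and T1. This adds variation unrelated to asthma.
2. **Test familiarity.** The intervention prompts the child to do the outcome test at home, whereas between-visit testing in the control arm is optional. If familiarity changes how a child blows, part of any T1 difference in FEV1:FVC would reflect familiarity and not asthma control.

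What is at stake is the reading of one secondary effect size that may be used to plan a later trial.

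**Working it through.** The documents give no power, SD or effect size for spirometry, so there is no figure to reproduce. The check is a comparison of the texts, followed by two calculations for scale.

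**Which difference follows arm?**
- Coaching versus app instructions follows visit mode. Both arms share the same remote procedure, and baseline is completed before assignment, so T0 mode cannot depend on arm. T1 and T2 modes can be chosen after assignment, but nothing in the documents shows that the choice depends on arm.
- Prompted versus optional home testing follows arm. It begins after T0, so the baseline score carries no information about it and adjustment for that score cannot remove it.
- A mode effect that is the same at T0 and T1 would be partly absorbed by baseline adjustment. A change of mode between visits would not.

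**Inputs.** The sample is "60 parent-child dyads in an eight-week pilot randomized controlled trial (RCT"). Equal allocation is assumed, giving 30 per arm. The SAP's 80% retention benchmark gives a lower case of 0.80 × 30 = 24 per arm. Assumed for illustration: outcome SD = 1 and a two-sided 0.05 level.

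**Standard error of a standardised difference**, √(2/n):
- n = 30: √(2/30) = 0.258
- n = 24: √(2/24) = 0.289

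**Visit mode as noise.** Let p be the remote share and g the assumed coaching effect in SD units. Extra variance is p(1−p)g².
- p = 0.25, g = 0.2: 0.25 × 0.75 × 0.04 = 0.0075 (0.8%)
- p = 0.25, g = 0.5: 0.25 × 0.75 × 0.25 = 0.047 (4.7%)
- p = 0.50, g = 0.2: 0.25 × 0.04 = 0.010 (1.0%)
- p = 0.50, g = 0.5: 0.25 × 0.25 = 0.0625 (6.2%)

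Chance imbalance in mode shifts the arm difference with SD g√(2p(1−p)/n). The smallest case is 0.2 × 0.112 = 0.022 (p = 0.25, n = 30). The largest is 0.5 × 0.144 = 0.072 (p = 0.50, n = 24). Both are small beside 0.258-0.289.

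**Test familiarity as a shift.** Suppose IMPACT has no true effect and familiarity alone shifts one arm by d SD. The reported effect size then moves by d. The chance of a nominally significant difference is Φ(d/SE − 1.96) + Φ(−d/SE − 1.96):

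| Assumed d | 30 per arm | 24 per arm |
|---|---|---|
| 0.1 | 6.7% | 6.4% |
| 0.2 | 12.1% | 10.7% |
| 0.3 | 21.3% | 18.0% |
| 0.5 | 49.1% | 41.0% |

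The nominal figure is 5%. For comparison, the half-width of a 95% interval is 1.96 × 0.258 = 0.51 at 30 per arm and 1.96 × 0.289 = 0.57 at 24 per arm. A shift of 0.1-0.3 SD would lie well inside that interval. None of these values of d comes from the documents.

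**The case against.** A reader might infer that the coaching gap itself biases the arm comparison. The documents do not support that: the gap follows visit mode, both arms share the remote procedure, and T0 mode is set before assignment. What remains is mainly noise, with the possibility that uncoached visits make any familiarity difference matter more.

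A reader might also infer that IMPACT children rehearse the test for eight weeks while controls do not, so that the comparison does mix practice with disease. That goes too far. No frequency or uptake of home testing is stated. Section 4.5 expects some use by all families. Unsupervised home blows need not improve technique, and no document reports a practice effect on FEV1:FVC in either direction. An early stop would shorten FVC and raise the ratio, while a slow start would lower FEV1 and reduce it.

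Nor do the documents say that coaching is withheld remotely. Staff are live on the call, the spirometer has visual incentives, and section 12.4 refers to procedure manuals and checklists that are not available here. This stands as a reason for moderate wording. It does not remove the point, because the protocol writes coaching into one procedure and app instructions into the other.

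Finally, the stakes are limited. The C-ACT and the primary outcomes (asthma responsibility and self-efficacy) do not depend on blowing technique. That also stands.

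**Conclusion.** The point holds as a cheap improvement. The two written procedures differ for an effort-dependent measure. On the assumptions above, this costs roughly 1-6% extra variance and produces no systematic arm difference. The separate contrast between prompted and optional home testing is related to arm and arises after randomisation. It creates a possible familiarity difference that the SAP's baseline adjustment cannot remove, and its size and direction are unknown.

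The plan also leaves little means of examining it afterwards. IMPACT app data include spirometer results (sections 5.4 and 5.5), but no count of home tests is described for controls.

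The conclusion rests on the protocol text as published. If the procedure manuals already require live coaching at remote visits, the visit-mode part falls away and only the familiarity part remains.

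**What to change.** 1. In the remote protocol (section 5.1), replace the sentence on following the app with one saying that the study team member already on the Zoom call coaches the child live, using the same script as in person, at T0, T1 and T2 in both arms.
2. Record visit mode at every visit. Ask families in both arms, with the same question, how many home spirometry tests the child has done since the last visit.
3. Reconcile section 4.5 (periodic use by all families) with the control text and the remote protocol in section 5.1 (device kept for study visits, extra use optional).
4. In the SAP, state that the spirometry effect size will be reported with a caveat about test familiarity. Any analysis limited to children seen in the same mode at T0 and T1 should be labelled descriptive, because T1 mode is chosen after randomisation and the restriction could introduce selection.

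The cost is a few minutes of staff time per remote visit, one extra question, one extra data field and minor wording changes.
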